4.2 Trial Treatments

The treatment to be used in this trial is outlined below in Table 2

Table 2 Trial Treatment

Drug	Dose/Potency	Dose Frequency	Route of Administration	Regimen/Treatment Period	Use
Pembrolizumab	200 mg	Q3W	IV infusion	Day 1 of each 3 week cycle	Experimental

Trial treatment should begin on the day of randomization or as close as possible to the date on which treatment is allocated/assigned.

4.2.1 Dose Selection/Modification

4.2.1.1 Dose Selection

The rationale for selection of doses to be used in this trial is provided in Section 4.0 – Background and Rationale.

Details on preparation and administration of pembrolizumab (MK-3475) are provided in the Pharmacy Manual.

4.2.1.2 Dose Modification (Escalation/Titration/Other)

Adverse events (both non-serious and serious) associated with pembrolizumab exposure may represent an immunologic etiology. These adverse events may occur shortly after the first dose or several months after the last dose of treatment. Pembrolizumab must be withheld for drug-related toxicities and severe or life-threatening AEs as per 3 below. See Section 5.6 for supportive care guidelines, including use of corticosteroids.

Table 3 Dose Modification Guidelines for Drug-Related Adverse Events

Toxicity	Hold Treatment For Grade	Timing for Restarting Treatment	Treatment Discontinuation
Diarrhea/Colitis	2-3	Toxicity resolves to Grade 0-1	Toxicity does not resolve within 12 weeks of last dose or inability to reduce corticosteroid to 10 mg or less of prednisone or equivalent per day within 12 weeks
	4	Permanently discontinue	Permanently discontinue
AST, ALT, or Increased Bilirubin	2	Toxicity resolves to Grade 0-1	Toxicity does not resolve within 12 weeks of last dose
	3-4	Permanently discontinue (see exception below) ^a	Permanently discontinue
Type 1 diabetes mellitus (if new onset) or Hyperglycemia	T1DM or 3-4	Hold pembrolizumab for new onset Type 1 diabetes mellitus or Grade 3-4 hyperglycemia associated with evidence of beta cell failure	Resume pembrolizumab when patients are clinically and metabolically stable
Hypophysitis	2-4	Toxicity resolves to Grade 0-1. Therapy with pembrolizumab can be continued while endocrine replacement therapy is instituted	Toxicity does not resolve within 12 weeks of last dose or inability to reduce corticosteroid to 10 mg or less of prednisone or equivalent per day within 12 weeks
Hyperthyroidism	3	Toxicity resolves to Grade 0-1	Toxicity does not resolve within 12 weeks of last dose or inability to reduce corticosteroid to 10 mg or less of prednisone or equivalent per day within 12 weeks
	4	Permanently discontinue	Permanently discontinue
Hypothyroidism		Therapy with pembrolizumab can be continued while thyroid replacement therapy is instituted	Therapy with pembrolizumab can be continued while thyroid replacement therapy is instituted
Infusion Reaction	2 ^b	Toxicity resolves to Grade 0-1	Permanently discontinue if toxicity develops despite adequate premedication
	3-4	Permanently discontinue	Permanently discontinue

Toxicity	Hold Treatment For Grade	Timing for Restarting Treatment	Treatment Discontinuation
Pneumonitis	2	Toxicity resolves to Grade 0-1	Toxicity does not resolve within 12 weeks of last dose or inability to reduce corticosteroid to 10 mg or less of prednisone or equivalent per day within 12 weeks
	3-4	Permanently discontinue	Permanently discontinue
Renal Failure or Nephritis	2	Toxicity resolves to Grade 0-1	Toxicity does not resolve within 12 weeks of last dose or inability to reduce corticosteroid to 10 mg or less of prednisone or equivalent per day within 12 weeks
	3-4	Permanently discontinue	Permanently discontinue
All Other Drug-Related Toxicity ^c	3 or Severe	Toxicity resolves to Grade 0-1	Toxicity does not resolve within 12 weeks of last dose or inability to reduce corticosteroid to 10 mg or less of prednisone or equivalent per day within 12 weeks
	4	Permanently discontinue	Permanently discontinue

Note: Permanently discontinue for any severe or Grade 3 drug-related AE that recurs or any life-threatening event.

^a For patients with liver metastasis who begin treatment with Grade 2 AST or ALT, if AST or ALT increases by greater than or equal to 50% relative to baseline and lasts for at least 1 week then patients should be discontinued.

^b If symptoms resolve within one hour of stopping drug infusion, the infusion may be restarted at 50% of the original infusion rate (e.g., from 100 mL/hr to 50 mL/hr). Otherwise dosing will be held until symptoms resolve and the subject should be premedicated for the next scheduled dose;

^c Patients with intolerable or persistent Grade 2 drug-related AE may hold study medication at physician discretion. Permanently discontinue study drug for persistent Grade 2 adverse reactions for which treatment with study drug has been held, that do not recover to Grade 0-1 within 12 weeks of the last dose.

Dosing interruptions are permitted in the case of medical / surgical events or logistical reasons not related to study therapy (e.g., elective surgery, unrelated medical events, patient vacation, and/or holidays). Subjects should be placed back on study therapy within 3 weeks of the scheduled interruption, unless otherwise discussed with the Sponsor. The reason for interruption should be documented in the patient's study record.

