4.1.3 Subject Exclusion Criteria

The subject must be excluded from participating in the trial if the subject:

1. Is currently participating and receiving study therapy or has participated in a study of an investigational agent and received study therapy or used an investigational device within 4 weeks of the first dose of treatment.
2. Have completed more than six (6) cycles of first line platinum doublet chemotherapy or more than six (6) have elapsed from the last chemotherapy administration of the first line chemotherapy with platinum doublet.
3. Has a diagnosis of immunodeficiency or is receiving systemic steroid therapy or any other form of immunosuppressive therapy within 7 days prior to the first dose of trial treatment.
4. Has a known history of active TB (Bacillus Tuberculosis)
5. Hypersensitivity to pembrolizumab or any of its excipients.
6. Has had a prior anti-cancer monoclonal antibody (mAb) within 4 weeks prior to study Day 1 or who has not recovered (i.e., \leq Grade 1 or at baseline) from adverse events due to agents administered more than 4 weeks earlier.
7. Has had prior chemotherapy, targeted small molecule therapy, or radiation therapy within 2 weeks prior to study Day 1 or who has not recovered (i.e., \leq Grade 1 or at baseline) from adverse events due to a previously administered agent.
 - Note: Subjects with \leq Grade 2 neuropathy are an exception to this criterion and may qualify for the study.
 - Note: If subject received major surgery, they must have recovered adequately from the toxicity and/or complications from the intervention prior to starting therapy.
8. Has a known additional malignancy that is progressing or requires active treatment. Exceptions include basal cell carcinoma of the skin or squamous cell carcinoma of the skin that has undergone potentially curative therapy or in situ cervical cancer.
9. Has known active central nervous system (CNS) metastases and/or carcinomatous meningitis. Subjects with previously treated brain metastases may participate provided they are stable (without evidence of progression by imaging for at least four weeks prior to the first dose of trial treatment and any neurologic symptoms have returned to baseline), have no evidence of new or enlarging brain metastases, and are not using steroids for at least 7 days prior to trial treatment. This exception does not include carcinomatous meningitis which is excluded regardless of clinical stability.

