4.5.2 Prohibited Concomitant Medications

Subjects are prohibited from receiving the following therapies during the Screening and Treatment Phase (including retreatment for post-complete response relapse) of this trial:

- Antineoplastic systemic chemotherapy or biological therapy
- Immunotherapy not specified in this protocol
- Chemotherapy not specified in this protocol
- Investigational agents other than pembrolizumab
- Radiation therapy
 - Note: Radiation therapy to a symptomatic solitary lesion or to the brain may be allowed at the investigator's discretion.

- Live vaccines within 30 days prior to the first dose of trial treatment and while participating in the trial. Examples of live vaccines include, but are not limited to, the following: **measles, mumps, rubella, varicella/zoster, yellow fever, rabies, BCG, and typhoid vaccine.**
- Systemic glucocorticoids for any purpose other than to modulate symptoms from an event of clinical interest of suspected immunologic etiology. The use of physiologic doses of corticosteroids may be approved after consultation with the Sponsor.

Subjects who, in the assessment by the investigator, require the use of any of the aforementioned treatments for clinical management should be removed from the trial. Subjects may receive other medications that the investigator deems to be medically necessary.

The Exclusion Criteria describes other medications which are prohibited in this trial.

There are no prohibited therapies during the Post-Treatment Follow-up Phase.

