4.6 Rescue Medications & Supportive Care

4.6.1 Supportive Care Guidelines

Subjects should receive appropriate supportive care measures as deemed necessary by the treating investigator. Suggested supportive care measures for the management of adverse events with potential immunologic etiology are outlined below. Where appropriate, these guidelines include the use of oral or intravenous treatment with corticosteroids as well as additional anti-inflammatory agents if symptoms do not improve with administration of corticosteroids. Note that several courses of steroid tapering may be necessary as symptoms may worsen when the steroid dose is decreased. For each disorder, attempts should be made to rule out other causes such as metastatic disease or bacterial or viral infection, which might require additional supportive care. The treatment guidelines are intended to be applied when the investigator determines the events to be related to pembrolizumab.

Note: if after the evaluation the event is determined not to be related, the investigator does not need to follow the treatment guidance (as outlined below). Refer to Section 5.2.1 for dose modification.

It may be necessary to perform conditional procedures such as bronchoscopy, endoscopy, or skin photography as part of evaluation of the event.

- **Pneumonitis:**
 - For **Grade 2 events**, treat with systemic corticosteroids. When symptoms improve to Grade 1 or less, steroid taper should be started and continued over no less than 4 weeks.
 - For **Grade 3-4 events**, immediately treat with intravenous steroids. Administer additional anti-inflammatory measures, as needed.

- Add prophylactic antibiotics for opportunistic infections in the case of prolonged steroid administration.
- **Diarrhea/Colitis:**

Subjects should be carefully monitored for signs and symptoms of enterocolitis (such as diarrhea, abdominal pain, blood or mucus in stool, with or without fever) and of bowel perforation (such as peritoneal signs and ileus).

 - All subjects who experience diarrhea/colitis should be advised to drink liberal quantities of clear fluids. If sufficient oral fluid intake is not feasible, fluid and electrolytes should be substituted via IV infusion. For Grade 2 or higher diarrhea, consider GI consultation and endoscopy to confirm or rule out colitis.
 - For **Grade 2 diarrhea/colitis**, administer oral corticosteroids.

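### Table 3 lets pembrolizumab restart at Grade 0-1 with no limit on the steroid dose, so a patient can be re-dosed on full-dose steroid

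*Combined protocol and SAP*

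**What the plan says.** In Section 4.2.1.2, Table 3, the restart cell for colitis Grade 2-3, AST/ALT/bilirubin Grade 2, hyperthyroidism Grade 3, pneumonitis Grade 2, renal failure or nephritis Grade 2, and all other drug-related toxicity Grade 3 or severe reads only "Toxicity resolves to Grade 0-1". The hypophysitis cell (Grade 2-4) says the same and adds that pembrolizumab may continue while endocrine replacement is started.

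A steroid level appears only in the discontinuation column, as "inability to reduce corticosteroid to 10 mg or less of prednisone or equivalent per day within 12 weeks". Six of the seven rows carry it. The AST/ALT/bilirubin row does not.

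Section 4.6.1 gives corticosteroids for each of the six named events at the grades listed. For Grade 3 colitis it specifies intravenous and then high-dose oral treatment. In every case the taper starts once the event is at Grade 1 or less and runs for at least 4 weeks. The same section warns: "Note that several courses of steroid tapering may be necessary as symptoms may worsen when the steroid dose is decreased".

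Elsewhere the protocol is stricter about steroids. Exclusion criterion 3 (Section 4.1.3) bars a patient "receiving systemic steroid therapy or any other form of immunosuppressive therapy within 7 days prior to the first dose of trial treatment". Section 4.5.2 prohibits "Systemic glucocorticoids for any purpose other than to modulate symptoms from an event of clinical interest of suspected immunologic etiology" and adds: "The use of physiologic doses of corticosteroids may be approved after consultation with the Sponsor".

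**The concern.** Restart eligibility and the start of the taper are triggered by the same observation, Grade 0-1. At that moment the steroid has not yet been reduced, and it may be what is holding the event down. Grade 0-1 on a full steroid dose does not show that the event has resolved, and the protocol itself expects that symptoms may return as the dose falls. Re-dosing then exposes the patient to the drug again before that is known.

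The permanent consequence is limited but real. The note under Table 3 says: "Permanently discontinue for any severe or Grade 3 drug-related AE that recurs or any life-threatening event". It bears on every row that allows a restart after Grade 3: colitis, hyperthyroidism, hypophysitis and all other toxicity. In those rows a return at Grade 3 costs the patient the drug for good. A return at Grade 2 does not by itself do so.

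**Working it through.** The plan states no figure on this point, so there is none to reproduce. The check is a reading of the steroid rules followed by a timing calculation.

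**Does any other rule block a restart on full-dose steroid?**

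- Table 3, discontinuation column: the 10 mg level applies at 12 weeks. A patient on 40 mg at week 4 has not breached it.
- Section 4.5 carries medications barred by the exclusion criteria into the trial period, and criterion 3 bars systemic steroids. However, criterion 3 is tied to the first dose, and the specific steroid rule in Section 4.5.2 exempts treatment of suspected immune-related events. The specific rule governs.
- Section 6.1.3 requires acceptable laboratory results before each dose. A steroid can be what makes AST or ALT acceptable, and laboratory tests do not grade colitis or pneumonitis.
- Section 4.6.1 refers back to the dose-modification section and adds no restart rule.
- The all-other row has no entry in Section 4.6.1, but its own 10 mg stop rule presupposes steroid use.

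Nothing in the documents supplied closes the gap.

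**How long is the window?**

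From the documents: the taper starts at Grade 1 or less and lasts at least 28 days (Section 4.6.1); dosing is every 21 days (Section 4.2.2). Assumed, because the documents do not say: the starting dose D (20, 40, 60 or 80 mg/day of prednisone or equivalent), a linear fall to zero, a taper length L of 28 or 42 days, and a 21-day dosing grid that runs on through the hold.

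- Days above 10 mg after Grade 0-1: T = L × (1 − 10/D). For D = 40 and L = 28, T = 28 × 0.75 = 21.0.
- Taper days remaining once the dose is at 10 mg: L − T.
- Doses deferred if 10 mg is required: the number of k ≥ 0 with u + 21k < T, where u (0 ≤ u < 21) is the number of days from Grade 0-1 to the next scheduled dose.

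| L (days) | D (mg) | T (days) | L − T (days) | Doses deferred |
|---|---|---|---|---|
| 28 | 20 | 14.0 | 14.0 | 0-1 |
| 28 | 40 | 21.0 | 7.0 | 1 |
| 28 | 60 | 23.3 | 4.7 | 1-2 |
| 28 | 80 | 24.5 | 3.5 | 1-2 |
| 42 | 20 | 21.0 | 21.0 | 1 |
| 42 | 40 | 31.5 | 10.5 | 1-2 |
| 42 | 60 | 35.0 | 7.0 | 1-2 |
| 42 | 80 | 36.8 | 5.2 | 1-2 |

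Even a full dosing interval after Grade 0-1 need not be enough. From 80 mg over 28 days, the day-21 dose is 80 × (1 − 21/28) = 20 mg. A patient already at 10 mg or less has a window of 0 days, and a taper that falls faster at first shortens the window. The minimum taper (28 days) is longer than the dosing interval (21 days), so at least one scheduled dose falls within the taper.

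**Does the 12-week rule catch these patients?**

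In these scenarios 10 mg is reached at most 36.8 days (5.25 weeks) after Grade 0-1. The stop rule therefore comes into play only if Grade 0-1 itself comes late, after week 12 − 5.25 = 6.75 at the earliest when the 12 weeks run from the last dose. Before that, nothing in Table 3 prevents a dose above 10 mg.

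**The case against.** The strongest reply is that the restart and discontinuation columns should be read together. A patient is stopped for failing either to resolve or to come down to 10 mg, so the hold naturally lasts until both are achieved. The table is headed as guidelines, the investigator may withhold or withdraw (Section 4.8), and a careful investigator would wait. Part of this stands: Table 3 permits an early restart and does not order one. But the restart column states its own condition, and that condition omits the steroid.

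Second, Section 6.1.2.1 sends the management of immune-related events to separate ECI guidance in Appendix 4, which is not among the documents supplied and may set a restart level. That limits what can be said about the whole protocol package. It does not repair Table 3, which is the operative dosing rule and should carry any such level.

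Third, every window above rests on assumed doses and taper shapes. That is correct. The conclusion needs only that some patients are above 10 mg when Grade 0-1 is first reached, which the high-dose oral steroid specified for Grade 3 colitis makes plausible.

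Fourth, deferring up to two doses is not trivial when the Trial Summary estimates an average of 6 cycles per patient. That is a fair statement of the cost, and it has to be set against a benefit whose frequency is unknown.

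**Conclusion.** The point holds as a restart rule that is too wide. Seven rows of Table 3 allow pembrolizumab to be given at Grade 0-1 with no steroid level, at the moment Section 4.6.1 begins the taper. Under the assumptions shown, the patient is above 10 mg for 14.0 to 36.8 days. It deserves correction as an inexpensive safety improvement.

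A reader might go further in three ways that the documents do not support.

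- That Table 3 contradicts Section 4.6.1. It does not: the two can be followed together, and one simply permits too much.
- That early restarts would distort 1-year irPFS. The documents give no rate of held events, restarts or recurrences, so neither a share of patients nor an effect on the endpoint can be derived.
- That the missing 10 mg stop limb in the AST/ALT/bilirubin row is itself an error to be put right. It is an inconsistency with the other steroid-treated rows, but adding the limb creates a new permanent stop, and the main point does not depend on it.

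The correction narrows the problem without removing it. A restart late in the taper, at 10 mg or less, remains possible.

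**What to change.** In the restart column of all seven rows, keep "Toxicity resolves to Grade 0-1" and add a second condition: if corticosteroids were given for the event, the daily dose has come down to no more than 10 mg of prednisone or equivalent. In the hypophysitis row, exempt physiologic replacement steroid and keep the existing sentence on endocrine replacement. If the ECI guidance sets a different restart level, use that level.

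The cost is a wording change to one table, with no new visit or test. Some restarts come later, by up to about two three-weekly doses under the taper assumptions above. In the six rows that already have the 10 mg stop limb, no restart is lost if its 12 weeks run from the last dose, because a patient above 10 mg at that point is already to be stopped. The limb does not state its starting point. Footnote c counts from the last dose ("that do not recover to Grade 0-1 within 12 weeks of the last dose"), but if sites count from a later date a few late restarts would be lost. In the AST/ALT/bilirubin row, the restart condition alone delays restarts and does not forbid them.

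Optional, for the sponsor to weigh: add the 10 mg, 12-week limb to the AST/ALT/bilirubin Grade 2 discontinuation cell. Counting from the last dose, the latest week of Grade 0-1 that still meets it is 12 − T/7. For a 28-day taper from 20, 40, 60 or 80 mg this is week 10.0, 9.0, 8.7 or 8.5. Patients who reach Grade 0-1 between then and week 12 may restart today and would be stopped.

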4.2.2 Timing of Dose Administration

Trial treatment should be administered on Day 1 of each cycle after all procedures/assessments have been completed as detailed on the Trial Flow Chart (Section 6.0). Trial treatment may be administered up to 3 days before or after the scheduled Day 1 of each cycle due to administrative reasons.

All trial treatments will be administered on an outpatient basis.

Pembrolizumab 200 mg will be administered as a 30 minute IV infusion every 3 weeks. Sites should make every effort to target infusion timing to be as close to 30 minutes as possible. However, given the variability of infusion pumps from site to site, a window of -5 minutes and +10 minutes is permitted (i.e., infusion time is 30 minutes: -5 min/+10 min).

The Pharmacy Manual contains specific instructions for the preparation of the pembrolizumab infusion fluid and administration of infusion solution.

4.2.3 Trial Blinding/Masking

This is an open-label trial; therefore, the Sponsor, investigator and subject will know the treatment administered.

SWIPE Protocol Version: 1.1 June, 2017

4.3 Randomization or Treatment Allocation

Not applicable

4.4 Stratification

Not applicable

4.5 Concomitant Medications/Vaccinations (allowed & prohibited)

Medications or vaccinations specifically prohibited in the exclusion criteria are not allowed during the ongoing trial. If there is a clinical indication for one of these or other medications or vaccinations specifically prohibited during the trial, discontinuation from trial therapy or vaccination may be required. The investigator should discuss any questions regarding this with the Merck Clinical team. The final decision on any supportive therapy or vaccination rests with the investigator and/or the subject's primary physician.

4.5.1 Acceptable Concomitant Medications

All treatments that the investigator considers necessary for a subject's welfare may be administered at the discretion of the investigator in keeping with the community standards of medical care. All concomitant medication will be recorded on the case report form (CRF) including all prescription, over-the-counter (OTC), herbal supplements, and IV medications and fluids. If changes occur during the trial period, documentation of drug dosage, frequency, route, and date may also be included on the CRF.

All concomitant medications received within 28 days before the first dose of trial treatment and 30 days after the last dose of trial treatment should be recorded. Concomitant medications administered after 30 days after the last dose of trial treatment should be recorded for SAEs and ECIs as defined in Section 7.2.

